3.3 Number of Sites and Subjects

This is a global, multicenter study in approximately 40 sites and 100 subjects.

3.4 Randomization and Blinding

Not applicable.

3.5 Safety Monitoring Committee

Not applicable.

3.6 Estimated Treatment Duration

Each subject's study participation may be up to 38 months or until the study is terminated (per Section 4.6), whichever occurs first. The study consists of a Screening Phase (1 month), Treatment Phase (36 months), and EOS Visit (30 [\pm 5] days after the last dose).

3.7 Definition of End of Study

The study is expected to be completed approximately 3 years after the last subject is enrolled. The study is considered completed with the last assessment for the last subject participating in the study or if the study is terminated, whichever occurs first, see Section 4.6.

4 SELECTION, DISCONTINUATION, AND WITHDRAWAL OF SUBJECTS

4.1 Inclusion Criteria

Subjects must meet *all* of the following criteria:

1. Completed the EOS Visit in Study NEOD001-201
2. Adequate bone marrow reserve, hepatic and renal function, as demonstrated by:
 - Absolute neutrophil count (ANC) $\geq 1.0 \times 10^9/L$
 - Platelet count $\geq 75 \times 10^9/L$
 - Hemoglobin ≥ 9 g/dL
 - Total bilirubin $\leq 2 \times$ upper limit of normal (ULN)
 - Aspartate aminotransferase (AST) $\leq 3 \times$ ULN
 - Alanine aminotransferase (ALT) $\leq 3 \times$ ULN
 - Alkaline phosphatase (ALP) $\leq 5 \times$ ULN (except for subjects with hepatomegaly and isozymes specific to liver, rather than bone)
 - Estimated glomerular filtration rate (eGFR) ≥ 25 mL/min/1.73 m² as estimated by the Chronic Kidney Disease Epidemiology Collaboration (CKD-EPI) equation, or measured GFR ≥ 25 mL/min/1.73 m²
3. Systolic blood pressure (BP) 80-180 mmHg
4. Women of childbearing potential (WOCBP) must have a negative pregnancy test during Screening and must agree to use highly effective physician-approved contraception ([Appendix 2](#)) from Screening to 90 days following the last study drug administration
5. Male subjects must be surgically sterile or must agree to use highly effective physician-approved contraception ([Appendix 2](#)) from Screening to 90 days following the last study drug administration
6. Ability to understand and willingness to sign an informed consent form (ICF) prior to initiation of any study procedures

4.2 Exclusion Criteria

Subjects must *not meet any* of the following criteria:

1. Any new medical contraindication or clinically significant abnormality on physical, neurological, laboratory, vital signs, or ECG examination (e.g., atrial fibrillation; *with the exception* of subjects for whom the ventricular rate is controlled) that precludes continuation or initiation of treatment with NEOD001 or participation in the study

2. Symptomatic orthostatic hypotension that in the medical judgment of the Investigator would interfere with subject's ability to safely receive treatment or complete study assessments
3. Myocardial infarction, uncontrolled angina, uncontrolled ventricular arrhythmias, or ECG evidence of acute ischemia, within 6 months prior to the Month 1-Day 1 Visit
4. Severe valvular stenosis (e.g., aortic or mitral stenosis with a valve area $<1.0 \text{ cm}^2$) or severe congenital heart disease
5. ECG evidence of acute ischemia or active conduction system abnormalities *with the exception* of any of the following:
 - First degree atrioventricular (AV) block
 - Second degree AV block Type 1 (Mobitz Type 1/Wenckebach type)
 - Right or left bundle branch block
 - Atrial fibrillation with a controlled ventricular rate (uncontrolled [i.e., $>110 \text{ bpm}$] ventricular rate is not allowed [determined by an average of three beats in Lead II or 3 representative beats if Lead II is not representative of the overall ECG])
6. Has not recovered (i.e., equivalent to a CTCAE \geq Grade 2) from the clinically significant toxic effects of prior anticancer therapy. **Exception:** subjects who have received treatment with a proteasome inhibitor such as bortezomib may have CTCAE Grade 2 neuropathy.
7. Received any of the following within the specified time frame prior to the Month 1-Day 1 Visit:
 - Oral or IV antibiotics, antifungals, or antivirals within 1 week, *with the exception* of prophylactic oral agents. Note: In the event that a subject requires the chronic use of antivirals, Medical Monitor permission is required for entry into the study.
 - Hematopoietic growth factors, transfusions of blood or blood products within 1 week
 - Chemotherapy, radiotherapy, HDAC inhibitors, or other plasma cell directed therapy within 2 weeks
 - ASCT within 4 weeks (i.e., ASCT is allowed if it occurred *before* enrollment in Study NEOD001-201 or *after* completion of Study NEOD001-201 if it was at least 4 weeks before Month 1-Day 1 of this study)
 - Major surgery within 4 weeks (or within 2 weeks following consultation with and approval of Medical Monitor)
 - Planned organ transplant during the study
 - Any investigational agent, other than NEOD001, within 4 weeks

- Any experimental imaging agent directed at amyloid within 2 years
8. Active malignancy *with the exception* of any of the following:
 - Adequately treated basal cell carcinoma, squamous cell carcinoma, or in situ cervical cancer
 - Adequately treated Stage I cancer from which the subject is currently in remission and has been in remission for ≥ 2 years
 - Low-risk prostate cancer with Gleason score < 7 and prostate-specific antigen < 10 mg/mL
 - Any other cancer from which the subject has been disease-free for ≥ 2 years
 9. History of Grade ≥ 3 infusion-related AEs or hypersensitivity to NEOD001
 10. History of severe allergy to any of the components of NEOD001 such as histidine/L-histidine, Trehalose, or Polysorbate 20
 11. Currently known uncontrolled bacterial, viral, fungal, HIV, hepatitis B, or hepatitis C infection
 12. Women who are breastfeeding
 13. Any condition which could interfere with, or the treatment for which might interfere with, the conduct of the study or which would, in the opinion of the Investigator, unacceptably increase the subject's risk by participating in the study
 14. Unable or unwilling to adhere to the study-specified procedures and restrictions
 15. Subject is under legal custodianship

4.3 Early Treatment Discontinuation

If the subject discontinues study drug prior to the EOS Visit, they should return for an ETD Visit 30 (± 5) days after their final administration of study drug as per Section 6.1.3. If a subject fails to return for the scheduled visit, a documented effort must be made to determine the reason. If the subject cannot be reached by telephone after 2 attempts, a certified letter will be sent to the subject (or the subject's legally authorized representative, if appropriate) requesting contact with the Investigator. This information will be recorded in the study records.

Reasons for early discontinuation from study drug treatment may include, but are not limited to:

- Need for organ transplant

- A suspected NEOD001-related clinically significant immunologic reaction – collect additional serum samples, if possible, during the period following the treatment stoppage to allow for the determination of the persistence of anti-NEOD001 antibodies. At a minimum, samples should be collected at the ETD Visit and 3 months after the ETD Visit, if the subject agrees to return to the clinic.
- Occurrence of an AE or clinically significant laboratory abnormality that, in the opinion of the Investigator, warrants the subject's permanent discontinuation from study drug treatment; the Medical Monitor should be notified as soon as possible of any discontinuation of study drug due to an AE
- Suspected or confirmed pregnancy or nursing during study treatment period. Female subjects whose pregnancy test is positive at the ETD Visit must be followed to term or until termination of the pregnancy (Section 7.4.2).

After the ETD Visit, vital status follow-up phone calls should be made per Section 6.3.

4.4 Early Termination from the Study

Early termination occurs if the subject fails to complete the entire study, through the EOS Visit. Subjects may withdraw their consent to participate in this study at any time without prejudice. The Investigator must withdraw from the study any subject who requests to be withdrawn. A subject's participation in the study may be discontinued at any time at the discretion of the Investigator in accordance with his/her clinical judgment. The Sponsor or its designee should be notified in a timely manner of all subject discontinuations. When possible, the tests and evaluations listed for the ETD Visit should be carried out.

Early termination from the study may occur if:

- In the opinion of the Investigator, the subject cannot safely participate in the procedures required by the protocol
- Subject withdraws consent
- Subject is unwilling or unable to comply with the study requirements
- Subject is lost to follow-up

Vital status will be collected within legal and ethical boundaries for all screened subjects and will be searched in public sources. During the study close-out period, survival status will be collected within legal and ethical boundaries for all subjects who withdrew participation from the study. If vital status is determined, the subject will not be considered lost to follow-up.

4.5 Replacement of Subjects

As this is an open-label study for subjects who completed Study NEOD001-201, no subjects will be replaced.

4.6 Termination of the Clinical Study, Investigator, or Study Site

The Sponsor reserves the right to terminate the study, participation of an individual Investigator, or a study site at any time for any reason. Conditions that may warrant termination include, but are not limited to:

- Clinical or administrative reasons
- Discovery of an unexpected, relevant, and/or unacceptable risk to subjects
- Sponsor's discontinuation of further development of the study drug
- Study drug becomes commercially available
- Failure of the Investigator to comply with the protocol, the requirements of the Institutional Ethics Committee/Institutional Review Board (IEC/IRB) or Competent Authority (CA), the Sponsor's procedures, or Good Clinical Practice (GCP) guidelines
- Inadequate recruitment of subjects by the Investigator

According to the study contract, the Investigator also reserves the right to terminate participation in the study.

5 TREATMENT OF SUBJECTS

5.1 Study Drug

Study drug consists of NEOD001.

5.1.1 Formulation and Packaging of NEOD001

The active study drug, NEOD001, is supplied as a sterile, lyophilized dosage form in a 20/25 mL vial containing 500 mg/vial NEOD001. After reconstitution with 9.6 mL of sterile water for injection (WFI), the vial will contain 50 mg/mL of NEOD001, 25 mM L-Histidine, 230 mM Trehalose, and 0.02% Polysorbate 20. The labelling will comply with applicable regulatory requirements.

5.1.2 Shipping, Storage, and Handling of NEOD001

NEOD001 will be shipped to clinical sites in individual cartons (one vial per carton). Upon receipt, a study staff member will place the NEOD001 in a refrigerator at a temperature ranging from 2°C to 8°C in a secure, locked location. Access to the NEOD001 should be strictly limited to the study staff. Neither the Investigator nor any member of the study staff will distribute any of the study supplies to any person who is not participating in this study.

If a study staff member becomes aware that the NEOD001 has not been properly handled (e.g., supply arrived at room temperature or was not placed in refrigerator upon receipt), follow the procedure outlined in the Pharmacy Manual or immediately contact the Study Monitor (contact information available in the Study Manual). In such an event, NEOD001 should be quarantined in a 2°C to 8°C refrigerator and must not be administered to any subject until the drug has been approved for use.

It is expected that the site staff will maintain refrigerator temperature logs in the investigational product storage area, recording the temperature at least once each working day.

Refer to Section 5.3 and the Pharmacy Manual for further details about shipping, storage and handling of NEOD001.

5.2 Accountability and Return of Study Supplies

The study drug will be dispensed at the discretion of the Investigator in accordance with the conditions specified in this protocol. It is the Investigator's responsibility to ensure that accurate records of study drug disposition and return are maintained.

All study drugs provided by the Sponsor or provided at the study center should be retained at the site until otherwise instructed in writing by the Sponsor. Upon completion of the study or termination of the investigational site, all unused vials of study drug supplied by the Sponsor can be destroyed locally as per local institutional guidelines and a copy of the destruction certificate supplied to the Sponsor or may be shipped to a depot designated by the Sponsor. Refer to the Pharmacy Manual for additional information.

5.3 Dosage, Preparation, and Administration

Study drug consists of NEOD001. The NEOD001 dose is 24 mg/kg; however, the maximum dose administered is not to exceed 2500 mg. Therefore, subjects with a weight of 104.2 kg or greater will receive the maximum dose of 2500 mg. The subject's weight during Screening may be used for calculation of the first dose. Subsequent doses may be calculated based on the current weight at that visit or using the Screening weight, based on the site's institutional guidelines. A change of $\pm 10\%$ from the weight being used for dosing should trigger recalculation of the dose based on the new weight unless thought to be exclusively due to fluid fluctuation (e.g., edema).

Each vial of 500 mg of NEOD001 will be reconstituted with 9.6 mL sterile WFI to a concentration of 50 mg/mL resulting in a buffered, isotonic, preservative-free solution with a total extractable volume of 10 mL. Study drug will be prepared in a 250 mL IV bag of 0.9% saline. The equivalent volume of reconstituted NEOD001 will be withdrawn prior to transferring the drug solution into the IV bag, such that the total IV bag volume will be 250 mL. Refer to the Pharmacy Manual for complete information on preparing and administering the study drug.

The Pharmacy Staff at each site will be responsible for preparing the study drug.

The study drug should only be administered in settings where emergency resuscitative equipment and personnel trained in the management of anaphylaxis are immediately available to treat systemic reactions under the direct supervision of a physician.

NEOD001 will be administered once every 28 days (a ± 5 -day window is allowed for visits starting after Month 1) over 60 (± 10) minutes unless a longer infusion duration was established for the individual subject in Study NEOD001-201. A minimum of 21 days between doses is required. The length of the infusion may be extended over a longer period of time if and when it is clinically indicated.

NEOD001 contains no antimicrobial preservatives. Once reconstituted, storage of study drug, inclusive of dilution and administration, should be limited to 24 hours under refrigerated conditions or 4 hours at room temperature. If it is anticipated that the infusion will extend beyond 4 hours, the reconstituted study drug should be split into multiple bags to ensure that no amount of reconstituted study drug will be at room temperature for longer than 4 hours (i.e., from the time of reconstitution of the vial to end of the infusion of a bag). The additional bag(s) should remain refrigerated until ready for use. The volume contained in the administration tubing should be completely flushed using 30 mL of 0.9% Sodium Chloride Injection (USP) after administration of study drug. The infusion line should NOT be used for blood draws.

Postdose Monitoring Period: All subjects will be closely monitored after completion of the study drug infusion as follows:

- If it has been < 60 days since the subject's last visit in Study NEOD001-201, the subject should be monitored according to the observation time established for the individual subject in Study NEOD001-201
- If it has been ≥ 60 days since the subject's last visit in Study NEOD001-201, the subject should be monitored for 90 (± 10) minutes for at least the first two infusions

- Beginning with the third infusion, the Investigator may decrease the monitoring time to no less than 60 minutes, if no infusion-related reactions were observed in the previous infusions and allowed per the IRB/IEC
- The Investigator may increase the monitoring time if deemed appropriate or per local standards. In the event of any clinical concerns or suspicious signs or symptoms after the infusion, the subject will remain under observation for as long as the Investigator deems it appropriate.

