Due to the limited number of infusion-site related reactions reported to date, premedication of subjects prior to the start of NEOD001 infusion is not required in the NEOD001-OLE001, NEOD001-201, and NEOD001-OLE251 protocols. As of 30 September 2016, 221 subjects had been dosed in the 4 completed or ongoing studies. In Study NEOD001-CL002 (VITAL), 129 subjects received a total of 534 infusions of blinded study drug (24 mg/kg NEOD001 plus standard of care or placebo plus standard of care). In Study NEOD001-201 (PRONTO), 23 subjects received a total of 51 infusions of blinded study drug (24 mg/kg NEOD001 or placebo). In Study NEOD001-001, 69 subjects received 994 infusions of NEOD001 (up to doses of 24 mg/kg) and 31 of these subjects had gone on to receive 59 infusions of 24 mg/kg NEOD001 in the open-label extension study (NEOD001-OLE001). In the completed Study NEOD001-001, 6 subjects experienced 9 infusion-site reactions were reported (6 subjects) and most (n=7; 78%) were classified as Grade 1. As noted above, 1 subject in the ongoing Study NEOD001-201 experienced an event of vasovagal syncope (characterized by bradycardia, hypotension, and syncope). Another aspect of safety monitoring in studies of NEOD001 has been a required postinfusion observation time ranging from 60 to 120 minutes. Studies NEOD001-201 and NEOD001-OLE251 allow for flexibility in monitoring time if no reactions are seen after the first 2 infusions, as described in Section 5.3.

Based on the data available to date, NEOD001 has been well tolerated as single-agent therapy in subjects with AL amyloidosis and no clinically significant safety signals have been identified.

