3 STUDY PLAN

3.1 Study Design

This is a global, multicenter, Phase 2b, open-label extension study of subjects with AL amyloidosis who had a hematologic response ([Appendix 1](#)) to first-line treatment for their amyloidosis (e.g., chemotherapy, ASCT) and completed Study NEOD001-201. Subjects in this study may receive concomitant chemotherapy (see Section [5.6.1](#)).

Subject screening will occur during the 28 days prior to the first administration of study drug (i.e., Month 1-Day 1 Visit), which may overlap with the last visit in Study NEOD001-201. If all eligibility requirements are met, the subject will be enrolled and Screening assessments will be completed. Screening assessments are listed in [Table 1](#).

Study visits will occur every 28 days based on scheduling from Month 1-Day 1. A ± 5 -day window is allowed for visits starting after Month 1. Subjects may receive up to 36 infusions of study drug. Subjects who discontinue study drug before the End of Study (EOS) Visit should have an Early Treatment Discontinuation (ETD) Visit 30 (± 5) days after their final administration of study drug.

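### Early entrants to the extension keep their NEOD001-201 observation time even if they received placebo there, so a first NEOD001 infusion can be watched for less time than a re-exposure

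*Protocol*

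**What the plan says.** The Postdose Monitoring Period list in Protocol Section 5.3 has four bullets. They do the following:

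- **Entry less than 60 days after the last NEOD001-201 visit:** "the subject should be monitored according to the observation time established for the individual subject in Study NEOD001-201".
- **Entry at 60 days or more:** 90 (±10) "minutes for at least the first two infusions".
- **From the third infusion:** the investigator may shorten observation, to not less than 60 minutes, if earlier infusions were free of reactions and the ethics committee allows it.
- **Discretion:** "The Investigator may increase the monitoring time if deemed appropriate or per local standards".

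No bullet refers to the treatment received in NEOD001-201.

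Three other places give the context. Section 1.2.2 describes the NEOD001-201 infusions as blinded, either NEOD001 24 mg/kg or placebo. It says that NEOD001-201 and this study "allow for flexibility in monitoring time if no reactions are seen after the first 2 infusions", and points to Section 5.3 for the detail. It also says that NEOD001 studies have had "a required postinfusion observation time ranging from 60 to 120 minutes". Section 3.1 places screening in the 28 days before the first dose, "which may overlap with the last visit in Study NEOD001-201".

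**The concern.** The rule treats a recent NEOD001-201 visit as evidence that the subject tolerates NEOD001. That is sound for a subject who received NEOD001 and unsound for one who received placebo, whose reaction-free infusions say nothing about the antibody.

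Former-placebo subjects are expected in this study. Section 1.3 says the extension lets completers receive active treatment, and Table 6 in SAP Section 9.3 reserves an extension column for subjects who had placebo in NEOD001-201. The under-60-day route is also expected, since screening can overlap the last parent-study visit and Table 1 gives that route its own column.

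The result is an inverted order of caution. A subject with months of NEOD001 behind them who returns after a gap of 60 days or more gets 90 minutes at each of two infusions. A subject who has never received the drug may get less. At stake is roughly minutes 60 to 90 after the first two NEOD001 infusions, which in this group would rest on investigator discretion and not on a protocol requirement. No endpoint or analysis is affected.

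**Working it through.** The plan states no figure to reproduce, so the check compares what Section 5.3 requires of two subjects at the first extension infusion.

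| | Former placebo, entry <60 days | Prior NEOD001, entry ≥60 days |
|---|---|---|
| Earlier NEOD001 exposure | None | Yes |
| Required observation | Time set in NEOD001-201 | 90 (±10) min |
| Infusions covered by the 90-minute rule | None | At least two |

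**Does another provision reset the carried-over time?**

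- Section 6.1.2 and Table 1 footnote 30 only refer back to Section 5.3.
- The third bullet of Section 5.3 limits further shortening. It does not restore a time already shortened in NEOD001-201.
- Required vital signs end at 60 (±10) minutes after the end of infusion. The extra 30-minute check applies at Month 1 only.
- Exclusion criterion 9, prior severe infusion-related events or hypersensitivity to NEOD001, cannot screen out a subject who never received NEOD001.
- Premedication is not required (Section 1.2.2).

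None of these closes the gap.

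**Shortfall per infusion** = max(0, 90 − carried-over time). The NEOD001-201 protocol is not among the documents, so the carried-over time is varied over the 60 to 120 minutes in Section 1.2.2.

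| Carried-over time (min) | Shortfall per infusion (min) | Over two infusions (min) |
|---|---|---|
| 60 | 90 − 60 = 30 | 2 × 30 = 60 |
| 75 | 90 − 75 = 15 | 2 × 15 = 30 |
| 90 | 0 | 0 |
| 120 | 0 | 0 |

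With the ±10-minute window, the 60-minute case gives 80 − 60 = 20 to 100 − 60 = 40 minutes per infusion.

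**Number affected.** The lower bound is 0. For an upper bound, take the planned enrolment of about 100 and an assumed placebo share of one third to one half, since the documents give no allocation ratio: 100 × 1/3 ≈ 33 to 100 × 1/2 = 50. If half of these both entered in under 60 days and had a shortened time (also assumed), the number is about 17 to 25.

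**Background rate.** In NEOD001-001, 6 of 69 subjects had infusion-site reactions: 6/69 = 8.7%, exact (Clopper-Pearson) 95% CI 3.3% to 18.0%. There were 9 reactions in 994 infusions, 9/994 = 0.9%, and 7 of the 9 (78%) were Grade 1.

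**The case against.** The strongest reply is that the shortfall is unproven. It needs a former-placebo subject whose time was actually set below 90 minutes in NEOD001-201, and the rule in that protocol is not available. The 60 to 120 minute range describes NEOD001 studies generally. This stands as a limit on size. It does not remove the defect, because Section 1.2.2 says NEOD001-201 allowed flexibility after two reaction-free infusions and ties it to Section 5.3, where the floor is 60 minutes.

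The subject counts rest on two stacked assumptions and are not evidence of how many were affected. The background rate concerns infusion-site reactions without onset times, so it does not show that any event fell in minutes 60 to 90. Section 1.2.2 also reports no dose-limiting toxicities, related serious adverse events or confirmed anti-drug antibodies in NEOD001-001. All of this keeps the stake small.

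The protocol never names 90 minutes as the standard for a first exposure, and 60 minutes lies within the range the programme has used. But the protocol does ask for 90 minutes at two infusions after a mere gap in treatment, and allows shortening in those subjects only from the third. It is hard to justify less for a subject with no exposure at all.

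The general safeguards are real. Vital signs run to about an hour after every infusion, any suspicious sign prolongs observation, and infusions may be given only where "emergency resuscitative equipment and personnel trained in the management of anaphylaxis are immediately available". None of them is specific to a first exposure, and lengthening observation is optional.

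**Conclusion.** The concern holds as a conditional gap in the wording of Section 5.3. Followed as written, the rule can give a former-placebo subject who enters early less observation at a first NEOD001 infusion than it requires for a re-exposed subject who enters late.

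The shortfall is 0 to 30 minutes per infusion against the nominal 90, depending on a carried-over time the documents do not give. Only former-placebo subjects who entered in under 60 days with a time already cut below 90 minutes are affected. Their number is unknown and may be zero. Given the remaining safeguards and the few, mostly Grade 1, reactions reported, this is a cheap improvement and not a serious safety failure. SAP Section 10 records that the NEOD001 programme was discontinued, which bears on whether an amendment is still practical but not on whether the rule is sound.

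**What to change.** Amend the first bullet of the Postdose Monitoring Period in Section 5.3 so that the NEOD001-201 observation time carries over only when receipt of NEOD001 in that study is confirmed. Every other early entrant, whether known to have had placebo or still blinded, would follow the existing 90 (±10) minute rule for at least the first two extension infusions, or keep the NEOD001-201 time if it was longer. The third and fourth bullets can stay, and Table 1 footnote 30 already refers to Section 5.3. The shortfall for a former-placebo early entrant then becomes zero.

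No unblinding is needed, because a subject whose arm is unknown defaults to 90 minutes. While NEOD001-201 remains blinded, that could be most early entrants. A simpler alternative with the same effect is to require at least 90 (±10) minutes for everyone's first two extension infusions.

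The cost is one sentence of protocol text and up to about 30 more minutes in clinic at two visits for the subjects concerned, including some who had already received NEOD001.
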